#### 9.1.2.2 Secondary

Secondary effectiveness outcomes:

- OS rate at 24 months after the index date
  - Percentage of patients who are still alive at 24 months after the index date
- OS
  - Time interval from the index date to the date of death from any cause
- ORR up to 24 months after the index date
  - Percentage of patients with complete response (CR) or partial response (PR), as best overall response up to 24 months after the index date according to the investigator assessment

- DCR up to 24 months after the index date
  - Percentage of patients with CR, PR, or stable disease (SD), as best overall response up to 24 months after the index date according to the investigator assessment
- DoR
  - DoR is defined as the time from the first CR or PR criteria met, whichever was reported earlier, until the date of documented overall disease progression

**Note:** CR, PR, SD, progressive disease (PD) will be defined as per Response Evaluation Criteria in Solid Tumours (RECIST) version 1.1 ([Eisenhauer 2009](#))

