### **9.2.4                   Frequency of Assessments**

The [Table 1](#) provides the Schedule of Assessments for this study. Patients who sign the ICF and meet all eligibility criteria during the screening will be enrolled in this study. The baseline visit will be at the index date, which is defined as the first administration date, after informed consent, of Avelumab plus Axitinib therapy to patients with advanced RCC. Baseline data will be collected at the index date. The screening visit and the baseline visit may or may not be on the same day.

Patients will attend the sites (hospitals) as per routine clinical practice at the discretion of the treating physician. Therefore, the timing of the visits may vary. Results from physical examinations, vital signs, and body weight will be collected upon availability. Data on treatment response will also be collected upon availability. Patients will be asked to provide HRQoL data using the NCCN-FACT Fksi-19 questionnaires available as electronic patient-reported outcomes (ePRO) questionnaires at the index date and at every third cycle of Avelumab treatment (intervals of about 6 weeks) thereafter, until the end of treatment or end of 24 months of study follow-up period, whichever occurs first. Patients can fill out HRQoL data (ePRO questionnaires) either at their homes or at sites (hospitals) during their scheduled visits as per their convenience. In

exceptional cases, the questionnaires on patient-reported HRQoL data can be completed on paper and transferred into electronic case report form (eCRF) afterwards.

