To determine OS rate at 24 months after the index date	Endpoint: Percentage of patients who are still alive at 24 months after the index date.	14.2
To assess duration of OS	Endpoint: Time interval from the index date to the date of death from any cause.	14.2
To evaluate objective response rate (ORR) and disease control rate (DCR) up to 24 months after the index date	Endpoints: 
Percentage of patients with complete response (CR) or partial response (PR), as best overall response (BOR) up to 24 months after the index date according to the investigator assessment.Percentage of patients with CR, PR, or stable disease (SD), as BOR up to 24 months after the index date according to the investigator assessment. BOR will be derived as documented BOR considering the order CR>PR>SD>Progressive Disease (PD).	14.2
To assess duration of response (DoR)	Endpoint: for patients with BOR of CR or PR only, is the time interval from the first CR or PR criteria met, whichever was reported earlier, until the date of documented overall disease progression. BOR will be derived as documented BOR	14.2

Objectives	Endpoints (Outcome Measures)	IAP section
To assess duration of progression-free survival (PFS) on Avelumab plus Axitinib therapy and progression-free survival 2 (PFS2) on Avelumab plus Axitinib therapy followed by the second-line treatment	Endpoints: 
 Time interval from the index date to the date of disease progression or death from any cause, whichever comes first. Time interval from the index date to the date of disease progression on second-line treatment or death from any cause, whichever comes first. 	14.2
To assess the health-related quality of life (HRQoL)	Endpoint: National Comprehensive Cancer Network/Functional Assessment of Cancer Therapy-Kidney Symptom Index 19 (NCCN-FACT FKSI-19) at the index date and at every 6 weeks thereafter, until the end of treatment (EOT) or end of 24 months of study follow-up period, whichever occurs first.	16.3

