
Table 5 Outcome and event dates for PFS2
			
Scenario	Date of event/censoring	Outcome	
PD or death after further subsequent anti-cancer therapy	Date of PD or death	Event	
PD before further subsequent anti-cancer therapy	Date of last adequate tumor assessment ^a documenting no PD after further subsequent anti-cancer therapy is given	Censored	

	No PD/Death	Date of last adequate tumor assessment ^a documenting no PD after further subsequent anti-cancer therapy is given	Censored		
	Treatment discontinuation due to 'Disease progression' without documented progression	Not applicable	Information is ignored. Outcome is derived based on documented progression only.		
	Study end for consent withdrawn without PD or death	Date of last adequate tumor assessment ^a documenting no PD after subsequent anti-cancer therapy is given	Censored		
	Study end for lost to follow-up without PD or death	Date of last adequate tumor assessment ^a documenting no PD after subsequent anti-cancer therapy is given	Censored		
^a If there are no adequate post-baseline assessments prior to the PD or death, then the time without adequate assessment should be measured from the index date; if the criteria were met the censoring will be on the index date.					
ORR	The ORR will be calculated along with the two-sided 95% CI using the Clopper-Pearson method. In addition, the frequency (number and percentage) of participants with BOR of CR, PR, SD, PD and NE will be tabulated. Investigator response will be used to determine the BOR up to 24 months derived as per documented BOR considering the order CR>PR>SD>PD. [REDACTED]				
DCR	DCR is defined as proportion of participants with BOR of CR, PR, SD and will be calculated along with the two-sided 95% CI using the Clopper-Pearson method. Investigator response will be used to determine the BOR up to 24 months derived as per documented BOR considering the order CR>PR>SD>PD. [REDACTED]				
DoR	DoR is defined, for participants with BOR CR or PR only, as the time interval from the first CR or PR criteria met, whichever was reported earlier, until the date of documented overall disease progression. BOR will be derived as documented BOR. [REDACTED] If a participant has not had the event, DoR is censored at the date of last adequate tumor assessment.				

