Table 8.3.1.10	TEAEs leading to death by Primary System Organ Class (SOC) and Preferred Term (PT)
Table 8.3.1.23	Frequency of Medical Intervention or Medications Used for the Management of Related TEAEs

RECIST v 1.1 Best overall response with confirmation for CR and PR

Overall response at first timepoint	Overall response at subsequent timepoint	Best overall response
CR	CR	CR
CR	PR	SD, PD or PR ^a
CR	SD	SD provided minimum criteria for SD duration met, otherwise, PD
CR	PD	SD provided minimum criteria for SD duration met, otherwise, PD
CR	NE	SD provided minimum criteria for SD duration met, otherwise, NE
PR	CR	PR
PR	PR	PR
PR	SD	SD
PR	PD	SD provided minimum criteria for SD duration met, otherwise, PD
PR	NE	SD provided minimum criteria for SD duration met, otherwise, NE
NE	NE	NE

^aIf a CR is truly met at first time point, then any disease seen at a subsequent time point, even disease meeting PR criteria relative to baseline, makes the disease PD at that point (since disease must have reappeared after CR). Best response would depend on whether minimum duration for SD was met. However, sometimes 'CR' may be claimed when subsequent scans suggest small lesions were likely still present and in fact the patient had PR, not CR at the first time point. Under these circumstances, the original CR should be changed to PR and the best response is PR.

MS100070 0110 IAP v1.0 2021124

eSign GxP

POWERED BY
Adobe Sign

eSign GxP

POWERED BY
Adobe Sign

eSign GxP

POWERED BY
Adobe Sign

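### In the readable text DCR counts stable disease seen at any time, so one early SD scan before progression is disease control and the rate depends partly on when sites scan

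*SAP*

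**What the plan says.** Protocol section 9.1.2.2 defines DCR as "Percentage of patients with CR, PR, or stable disease (SD), as best overall response up to 24 months after the index date", judged by the investigator. Its note says that the response categories "will be defined as per Response Evaluation Criteria in Solid Tumours (RECIST) version 1.1"; it states no minimum interval for SD.

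SAP section 14.2 repeats the definition ("DCR is defined as proportion of participants with BOR of CR, PR, SD and will be calculated along with" a Clopper-Pearson interval) and gives the rule that produces BOR: "Investigator response will be used to determine the BOR up to 24 months derived as per documented BOR considering the order CR>PR>SD>PD". The endpoint table in SAP section 5 has the same rank-order rule. Neither readable text attaches a time condition to SD. A redacted block follows the rule in 14.2.

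The table in SAP section 18 is headed "RECIST v 1.1 Best overall response with confirmation for CR and PR". Several of its rows give the result as "SD provided minimum criteria for SD duration met, otherwise, PD", or NE in place of PD. No readable passage in either document says what the minimum is. The modification history (SAP section 3) records that rules for confirmed best response were added and that documented response is primary.

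On timing, Protocol section 9.2.4 says: "Data on treatment response will also be collected upon availability". Visits follow routine practice.

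**The concern.** A rank-order BOR with no time condition lets a single SD entry decide the classification, however soon after the index date it was recorded and whatever the next scan shows. In a trial with fixed imaging, the first scheduled scan acts as an implicit minimum. This study has no imaging schedule, so nothing takes that role. Two patients with the same disease course can be classed differently only because one was scanned early.

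The index date makes early scans more likely. It is the first administration after consent, and patients have by then received 1 or 2 cycles (Protocol sections 9.1.1 and 9.2.1). A scan timed from the real start of treatment falls sooner after the index date.

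DCR is a secondary outcome and the only response endpoint selected for subgroup analysis (SAP sections 8.2 and 14.2). The Clopper-Pearson interval covers sampling error, not this dependence on scan timing.

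**Working it through.** **No figure to reproduce.** The readable documents give no expected DCR, no imaging interval and no rate of early SD. The check therefore applies the stated rule to example sequences, then shows how far DCR moves per patient.

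**Step 1: the documented-BOR rule.** Rank CR > PR > SD > PD and take the best.

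| Scans after the index date | BOR | Counted in DCR |
|---|---|---|
| SD at week 3, PD at week 9 | SD | yes |
| PD at week 9 only | PD | no |
| SD at week 3, then NE | SD | yes |

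The first two rows can be the same disease course. Only the presence of the week 3 scan differs.

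**Step 2: the appendix table.** The rows that carry the SD-duration condition are CR then SD, CR then PD, CR then NE, PR then PD, and PR then NE; the footnote to CR then PR also refers to it. All start with CR or PR. PR then SD gives SD with no condition. No row starts with SD, so SD then PD is not covered. The minimum itself is undefined, so the conditional rows cannot be programmed from the readable text.

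**Step 3: is there a floor elsewhere?** The first analysis-visit window in SAP section 9.7 opens at day 45. It maps visits, leaves earlier ones to discussion rather than excluding them, and is not cited in the BOR rule. It is not a floor for SD.

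**Step 4: shift from the earlier cycles.** An Avelumab cycle is 2 weeks (SAP section 13). One or two cycles before the index date are 1 × 14 = 14 to 2 × 14 = 28 days, so time from the index date understates time on treatment by roughly 2 to 4 weeks.

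**Step 5: effect per patient.** The planned size is about 100 (Protocol section 9.5), and missing results stay in the denominator (SAP section 9). Moving one patient from SD to PD or NE changes DCR by 1/100 = 1 point. In a subgroup category of 20, the pooling threshold in SAP section 8.2, it is 1/20 = 5 points.

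**Step 6: illustration.** The exact 95% limits for x of n are the 2.5% quantile of Beta(x, n−x+1) and the 97.5% quantile of Beta(x+1, n−x). Take an assumed documented DCR of 80/100, and let k be the assumed number of patients whose only non-PD result is an SD before the minimum:

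| k | DCR | Exact 95% CI |
|---|---|---|
| 0 | 80% | 70.8% to 87.3% |
| 2 | 78% | 68.6% to 85.7% |
| 5 | 75% | 65.3% to 83.1% |
| 10 | 70% | 60.0% to 78.8% |

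From an assumed 70/100 (60.0% to 78.8%), k = 5 gives 65% (54.8% to 74.3%).

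**The case against.** **Redaction.** A block is blacked out directly after the DCR rule, and the title of the output next to the ORR and DCR table is blacked out too. A minimum could be there, so a reader should not infer that the plan has none. Against this, blocks also follow the documented-BOR rule under ORR and DoR, where an SD minimum would have no role, and the readable endpoint table in SAP section 5 carries none. The sponsor can settle it. The point is limited to the readable text.

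**RECIST 1.1 by reference.** Both documents name it. Whether it settles SD duration cannot be checked from them, and the readable documented-BOR rule does not invoke a duration.

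**The appendix.** A reader might infer that the SAP contradicts itself. It does not: the table governs confirmed BOR, DCR uses documented BOR, and that choice is recorded. What stands is an undefined term and a sequence that neither readable rule addresses with a minimum.

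**Low stakes.** All analyses are descriptive and the subgroups exploratory. The full BOR distribution is tabulated, and PFS registers the early progression. The protocol abstract applies its key-secondary label to all its secondary outcomes, so it gives DCR no special rank. Protocol section 9.9 concedes that real-world response may be less accurate and timely. All this is fair and limits the weight of the point. It does not remove the dependence of DCR on scan timing.

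**Conclusion.** The point holds on the readable text. The documented-BOR rule has no minimum time for SD, imaging is unscheduled, and one early SD followed by PD therefore counts as disease control. The SD-duration term in the appendix is undefined and would not cover that sequence even if it were defined.

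The size is unknown. A reader might infer a definite inflation of several points, but the documents give no early-SD rate, no scan-timing data and no expected DCR. Only the per-patient effect is established: 1 point at n=100. The counts in the illustration are assumptions. The effect is confined to DCR, its subgroup analyses and the SD/PD/NE split of the BOR table; the primary OS rate and documented ORR do not change. The conclusion also assumes that no minimum is set in the redacted text. If one is there, what remains is to confirm its value, its anchor and its scope.

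**What to change.** Before database lock, add to SAP section 14.2:

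- one minimum interval for SD to count in BOR, used in both the documented and the confirmed derivation;
- its anchor, either the index date or the actual start of treatment, given the 1 or 2 earlier cycles;
- the classification of an SD seen only before the minimum: PD if the next assessment is PD, NE if there is no later assessment;
- DCR without the minimum as a sensitivity row.

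The sponsor should justify the value from the imaging interval expected in routine care. A value such as 42 days is only an example: the plan's 6-week interval is the HRQoL questionnaire schedule, not a scan interval. If the redacted text already sets a minimum, it is enough to confirm these items and refer to it from the appendix.

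The cost is a short SAP addition and little programming. DCR may be slightly lower, and a few patients move to PD or NE. A minimum does not remove all dependence on scan timing: an SD just before the minimum with PD only much later would be classed as PD. The sensitivity row shows how much this matters.

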14.2 Further Endpoints

Endpoint Derivations

OS Rate at 24 months	OS rate is defined as the percentage of patients who are alive at 24 months after the index date. OS rate will be presented along with 95% CI.
-----------------------------	--

	Percentage of patients alive at the time of outcome assessment (24 months) will be calculated as per the KM approach.
OS	
OS is defined as the time from index date to the date of death due to any cause. OS for participants without death prior to cut-off will be censored at date of last contact. OS in months is calculated as follows:
 $\text{OS (months)} = [\text{date of death or censoring} - \text{index date} + 1] / 30.4375$ 
Note: If death events occurring after cut-off are to be taken into account, the table below may be used for OS. Nevertheless, this will not be the standard process.
 
OS will be estimated by the KM method. The percentage of censored patients will also be reported. Median event time will be reported, along with 25th and 75th percentiles. Percentage of patients experiencing event or being event-free at applicable timepoints will also be reported along with the corresponding two-sided 95% CIs.
 
Analyses of overall survival time

PFS	
PFS time is defined as the time from index date to the date of the first documentation of objective PD or death due to any cause, whichever occurs first. The tumor response will be determined according to Response Evaluation Criteria in Solid Tumours (RECIST) v 1.1 and assessed by the investigator.
 $\text{PFS time (in months)} = (\text{Date of PD or death} - \text{index date} + 1) / 30.4375 \text{ (months)}$

PFS data will be censored on the date of the last adequate tumor assessment for participants who do not have an event (PD or death) or start a subsequent anti-cancer therapy prior to an event. Participants who do not have any post-baseline tumor assessments will be censored on the start date.

The last adequate tumor assessment is defined as the last tumor assessment result that is not “NE” or “NA”.

The censoring and event date options to be considered for the PFS analysis is presented in below table.

PFS will be estimated by the KM method. The percentage of censored patients will also be reported. Median event time will be reported, along with 25th and 75th percentiles. Percentage of patients experiencing event or being event-free at applicable timepoints will also be reported along with the corresponding two-sided 95% CIs.

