Table 4 Outcome and event dates for PFS

Scenario	Date of event/censoring	Outcome
PD or death before subsequent anti-cancer therapy	Date of PD or death	Event
PD or death after subsequent anti-cancer therapy	Date of last adequate tumor assessment ^a documenting no PD before subsequent anti-cancer therapy is given	Censored
No PD/Death	Date of last adequate tumor assessment ^a documenting no PD before subsequent anti-cancer therapy is given	Censored
Treatment discontinuation due to 'Disease progression' without documented progression	Not applicable	Information is ignored. Outcome is derived based on documented progression only.
Study end for consent withdrawn without PD or death	Date of last adequate tumor assessment ^a documenting no PD before subsequent anti-cancer therapy is given	Censored

	Study end for lost to follow-up without PD or death	Date of last adequate tumor assessment ^a documenting no PD before subsequent anti-cancer therapy is given	Censored
^a If there are no adequate post-baseline assessments prior to the PD or death, then the time without adequate assessment should be measured from the index date; if the criteria were met the censoring will be on the index date.			
PFS2	
PFS2 time is defined as the time from the index date to the date of disease progression on second-line treatment or death from any cause, whichever comes first. The tumor response will be determined according to RECIST v 1.1 and assessed by the investigator.
 
PFS2 time (in months) = (Date of PD or death after second-line treatment start – index date + 1) / 30.4375 (months).
 
PFS2 data will be censored on the date of the last adequate tumor assessment for participants who do not have an event (PD or death) or start a further subsequent anti-cancer therapy prior to an event. Participants who do not have any post-baseline tumor assessments will be censored on the start date.
 
The last adequate tumor assessment is defined as the last tumor assessment result that is not “NE” or “NA”.
 
The censoring and event date options to be considered for the PFS2 analysis are presented in below table.
 
PFS2 will be estimated by the KM method. The percentage of censored patients will also be reported. Median event time will be reported, along with 25th and 75th percentiles. Percentage of patients experiencing event or being event-free at applicable timepoints will also be reported along with the corresponding two-sided 95% CIs.
		

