	
DoR (months) = [date of event or censoring–date of first CR or PR +1]/30.4375
 
DoR will be estimated by the KM method. The percentage of censored patients will also be reported. Median event time will be reported, along with 25th and 75th percentiles. Percentage of patients experiencing event or being event-free at applicable timepoints will also be reported along with the corresponding two-sided 95% CIs.

Table 6 **Outcome and event dates for DoR**

Scenario	Date of event/censoring	Outcome
PD before subsequent anti-cancer therapy	Date of PD	Event
PD after subsequent anti-cancer therapy	Date of last adequate tumor assessment ^a documenting no PD before subsequent anti-cancer therapy is given	Censored
No PD/Death	Date of last adequate tumor assessment ^a documenting no PD/Death before subsequent anti-cancer therapy is given	Censored
Treatment discontinuation due to 'Disease progression' without documented progression	Not applicable	Information is ignored. Outcome is derived based on documented progression only.
Study end for consent withdrawn without PD	Date of last adequate tumor assessment ^a documenting no PD before subsequent anti-cancer therapy is given	Censored
Study end for lost to follow-up without PD	Date of last adequate tumor assessment ^a documenting no PD before subsequent anti-cancer therapy is given	Censored

^a If there are no adequate post-baseline assessments prior to the PD, then the time without adequate assessment should be measured from the index date; if the criteria were met the censoring will be on the index date.

T2LT

T2LT is defined as the time from the last dose of Avelumab plus Axitinib to the start date of second-line treatment for RCC.

	T2LT time (in months) = (Second-line treatment start date – last dose of Avelumab plus Axitinib + 1)/ 30.4375 (months)
--	--

	T2LT will be summarized by descriptive statistics for continuous variables.
--	---

The subgroup analyses will be performed on selected secondary endpoints (OS, DCR, PFS, and PFS2) based on the analysis set for all subgroup levels defined in [Section 8.2](#) “Subgroup definition and parametrization”. All the subgroup analyses are exploratory and will be performed unstratified.

No adjustment for multiplicity will be performed. In the case of a low number of participants within a category of the analysis set, the categories will be pooled when meaningful (see [Section 8.2](#)).

15 Safety Analyses

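### Duration of response counts only documented progression as an event, so a responder's death without it is censored although PFS counts the same death

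*SAP*

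**What the plan says.** The SAP (14.2, DoR) measures "the time interval from the first CR or PR criteria met, whichever was reported earlier, until the date of documented overall disease progression", among participants with a best response of CR or PR. SAP section 5 and the protocol abstract give the same definition. Protocol 9.1.2.2 likewise runs DoR "until the date of documented overall disease progression". None of them names death.

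The censoring sentence in SAP 14.2 reads "If a participant has not had the event, DoR is censored at the date of last adequate tumor assessment". In Table 6 the only scenario with outcome Event is "PD before subsequent anti-cancer therapy". Death appears in one row only, labelled No PD/Death, which is censored at the last adequate assessment "documenting no PD/Death before subsequent anti-cancer therapy is given". For treatment stopped because of progression that was not documented, Table 6 says "Information is ignored. Outcome is derived based on documented progression only".

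PFS in the same section is "the time from index date to the date of the first documentation of objective PD or death due to any cause, whichever occurs first", and the event row of Table 4 is "PD or death before subsequent anti-cancer therapy". The PFS2 definition also includes death from any cause.

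Protocol 9.7.2 groups OS, PFS, PFS2 and DoR together and describes the Kaplan-Meier percentage at 12 or 24 months as the percentage of patients alive.

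**The concern.** Two time-to-event endpoints reported side by side treat the same death differently, and the plan does not point this out. Readers usually take DoR as time in response while alive, and the wording of protocol 9.7.2 encourages that reading. Under the planned rule, a responder who dies without a documented progression leaves the risk set at the last scan, as if the response could have continued.

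Such deaths are plausible here. Response data are collected as available rather than on a fixed imaging schedule (protocol 9.2.4 and Table 1), and protocol 9.9 concedes that RECIST assessment may be less accurate and timely than in a randomized trial. SAP 15.2.1 records progressive disease as a possible cause of death. A responder recorded as dying of progressive disease could therefore still be censored for DoR as not progressed.

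What is at stake is how the median DoR and the event-free percentages are interpreted, and whether they can be compared with PFS in the same patients.

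**Working it through.** **1. One patient under both rules.** Take a responder with first PR at month 3, last adequate scan at month 6, death at month 8, no documented progression and no new therapy.

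- Table 4: PFS event at month 8.
- DoR as planned: censored at month 6, that is 6 - 3 = 3 months after first response.
- DoR with death counted: event at 8 - 3 = 5 months.

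**2. Is there another rule for this death?** Table 6 shares the No PD/Death label with Table 4, where it can only mean neither event, because the first row of Table 4 makes death an event. Read that way in Table 6, death without progression has no row of its own. Read as no progression, or death, it is censored. The sentence before the table settles the outcome: without the event, the patient is censored. Table 6 also drops the words for death that Table 4 carries in its withdrawal row, its lost-to-follow-up row and its footnote. The wording is unclear, but on no reading is the death an event.

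**3. Size.** The documents state no DoR median, event count or death share, so there is no planned figure to reproduce. Everything below is an illustration under constant, independent hazards.

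Let w be the share of first events (progression or death) that are deaths without documented progression. The progression hazard is then (1 - w) times the total hazard, so

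- progression-only median = (progression-or-death median) / (1 - w)
- progression-only rate at t = (progression-or-death rate at t)^(1 - w)

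With an assumed progression-or-death median of 12 months, the 12-month rate with death counted is 50.0%, and:

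| w | factor on median | median as planned (months) | 12-month rate as planned |
|---|---|---|---|
| 5% | 1.05 | 12.6 | 51.8% |
| 10% | 1.11 | 13.3 | 53.6% |
| 20% | 1.25 | 15.0 | 57.4% |
| 30% | 1.43 | 17.1 | 61.6% |

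**4. Same model, other starting point.** Assume a progression-only median of 20 months and a rate of death without documented progression equal to r times the progression rate. The 12-month event-free rate is 2^(-12(1+r)/20).

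- As planned (deaths censored): 2^(-0.60) = 66.0%
- Death counted, r = 0.1: 2^(-0.66) = 63.3%
- Death counted, r = 0.2: 2^(-0.72) = 60.7%
- Death counted, r = 0.3: 2^(-0.78) = 58.2%

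The gap is 2.7 to 7.8 points (66.0 - 63.3 and 66.0 - 58.2).

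**5. Simulation at the study's size.** About 100 patients (protocol 9.5) at the 51.4% response rate that protocol section 7 cites for this combination gives about 51 responders. Assumptions: scans every 3 months, response at month 3 or 6, follow-up to 24 months from index, a progression-or-death median of 12 months, and 1000 runs per setting. At w = 20% the mean 12-month rate was 57.3% under the planned rule and 49.9% with death as an event. In no run was the planned 12-month estimate the lower of the two.

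**The case against.** The strongest reply is that a progression-only endpoint is legitimate. The protocol and SAP state it consistently, so it may be a choice rather than a slip. This stands: the planned curve reads long only relative to a progression-or-death definition. What does not stand is leaving the narrower endpoint unlabelled beside PFS, and described in protocol 9.7.2 as a percentage alive.

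A reader might infer that the figures above demonstrate bias from informative censoring. They do not. The model takes progression and death as independent, and in that model the planned curve is valid for time to progression. The gap is between two endpoint definitions. Informative censoring may well occur in practice, but the documents contain nothing that would measure it.

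A reader might also infer that the SAP gives no rule at all for a death without progression. It does, through the sentence before Table 6. The table is only unclear.

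A 24-month DoR rate would show a larger gap, but it should not be used. Follow-up ends 24 months from index, so a response first seen at month 3 leaves at most 24 - 3 = 21 months of observable duration. For the same reason, a 20-month median would barely be reached.

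Further points in the plan's favour hold:

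- The death shares are assumptions. At 5% the median is only about 5% longer.
- The group is narrow: responders who die without documented progression and before new therapy.
- With about 51 responders, the 95% half-width of a 12-month rate near 66% is about 1.96 × sqrt(0.66 × 0.34 / 51) = 13 points, ignoring censoring. That is wider than the gap.
- The percentage censored and a table of censoring and event status are planned, and OS and PFS, which count death, are reported alongside.

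These points limit the consequence. They do not remove the mismatch, which shifts the estimate in one direction.

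**Conclusion.** The point holds as a mismatch of definition. A responder who dies without documented progression and before new therapy is censored for DoR, while PFS counts the same death, and protocol 9.7.2 describes a quantity that the DoR curve cannot estimate. Relative to a progression-or-death definition, the planned median is longer by a factor of 1/(1-w): about 1.05, 1.11 and 1.25 at shares of 5%, 10% and 20%. With a 20-month progression-only median, the 12-month rate reads 66.0% instead of 63.3%, 60.7% or 58.2% when the death rate is 10%, 20% or 30% of the progression rate.

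These sizes rest on constant, independent hazards and on assumed medians and death shares; with few such deaths the effect is small. DoR is descriptive and secondary, so no test, sample size or primary result is affected. Part of the SAP's DoR entry is redacted, and nothing here depends on it. The change should be made because it is cheap and alters a reported estimate.

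**What to change.** Define DoR as time from first CR or PR to documented progression or death from any cause, whichever comes first. Then:

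- In SAP Table 6, add a row: death without PD, before subsequent anti-cancer therapy; date of death; Event. State that deaths after subsequent therapy are censored as in Table 4.
- Make clear that the No PD/Death row means neither PD nor death. Extend the withdrawal and lost-to-follow-up rows and the footnote from PD to PD or death.
- Align the protocol abstract, protocol 9.1.2.2 and SAP section 5. In protocol 9.7.2, describe the DoR percentage as alive and progression-free.

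If the progression-only version is kept, label it time to progression among responders, report how many responders died without documented progression, and correct the wording of protocol 9.7.2.

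No new data are needed, because death dates are already required for OS and PFS. The cost is a few lines of text and a slightly less favourable DoR.
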